8.4 Follow-up period

15 March 2022, page 118/216

The follow-up period includes the EOS visit 30 days after the last day of study treatment intake.

8.4.1 EOS Visit

This visit will be conducted 30–44 days after the permanent discontinuation of study treatment. All assessments should be conducted within the visit window. The last assessment conducted for the study will define the visit date.

The EOS visit should also be conducted for subjects who have switched to commercially available ponesimod.

The visits include:

- EDSS/FS
- MS relapse
- Recording of changes in concomitant medications
- Assessment and recording in the eCRF of methods of contraception (for WOCBP only)
- Body temperature
- SBP/DBP
- 12-lead ECG
- Ophthalmological examination (under the responsibility of the ophthalmologist)
- OCT (under the responsibility of the ophthalmologist)⁶
- Spirometry
- DL_{CO} (if applicable; under the responsibility of the pulmonologist)
- Hematology, blood chemistry, and (following approval of protocol version 5) a serum sample for immunogenicity evaluations (e.g., anti SARS-CoV-2 antibody testing) will be collected for all subjects
- Urinalysis
- Serum pregnancy test for WOCBP
- Recording of AEs and SAEs
- Remind WOCBP and fertile men to use the methods of contraception defined for this study until 6 weeks after the first of two consecutive tests confirming plasma teriflunomide level <0.02 mg/L[#] if such test results have not been obtained prior to EOS visit.

Important note: Teriflunomide testing is no longer required with the approval of protocol version 5

Scheduled OCT assessments are only applicable to Global Protocol version 1 to 5. The requirement for OCT assessments was removed from Protocol Version 6 onwards.

EudraCT 2016-004719-10 EDMS-ERI-207656619

Confidential

8.5 Unscheduled visits

15 March 2022, page 119/216

An unscheduled site visit may be performed at any time during the study (between scheduled visits), as necessary, at the investigator's discretion, or may be required such as in the case of a planned pregnancy. These visits include (but are not limited to) those performed due to safety (e.g., occurrence of an AE, laboratory abnormalities, planned study treatment interruption), administration of study treatment (e.g., re-initiation, return of unused study medication, need to initiate treatment with a QT-prolonging drug), and/or MS related issues (e.g., relapses).

The date of the visit and the reason for such visits as well as any data related to study assessments performed at unscheduled visits will be recorded in the eCRF.

8.5.1 Unscheduled visits for relapses (Visits R1, R2, etc.)

Subjects will be reminded to contact their treating neurologist at the clinical site immediately in the event of appearance of any new or worsened neurological symptoms. Whenever a subject contacts the principal investigator / treating neurologist reporting the appearance of any symptoms suggestive of an MS exacerbation, the principal investigator / treating neurologist will interview the subject and determine the necessity of an unscheduled visit for relapse. An unscheduled visit will be organized as soon as possible after onset or worsening of the symptom(s) as follows:

- The principal investigator / treating neurologist will interview and examine the subject to determine whether or not a relapse may have occurred since last visit using the dedicated relapse assessment questionnaire [see Appendix 10] and the relapse symptoms form [see Appendix 11] and decide whether the subject has to be referred to the efficacy assessor.
- In order to exclude potential other reasons for the symptom(s) observed, the principal investigator / treating neurologist will need to perform the following assessments:
 - Physical examination
 - Vital signs: SBP/DBP, pulse rate, body temperature
- In the event of the subject's referral to the efficacy assessor, the latter will perform the EDSS and FS within 7 days from the onset or worsening of the symptom(s). The decision regarding whether the new or worsened neurological symptoms are considered as confirmed or unconfirmed relapse will be made by the principal investigator / treating neurologist by assessing the compatibility of the symptoms reported by the subject and the presence or absence of a qualifying increase in the EDSS/FS (i.e., and increase of the magnitude described in Section 6.1.1) resulting from comparison between the current and previous, clinically stable EDSS/FS assessment performed by the efficacy assessor.

All MS relapses, whether confirmed or unconfirmed during the study, must be reported on specific relapse pages of the eCRF. MS relapses and associated symptoms are not to be entered on the AE page of the eCRF with the following exceptions:

EudraCT 2016-004719-10 EDMS-ERI-207656619

Confidential

15 March 2022, page 120/216

MS relapses with fatal outcome (these must always be recorded as AEs on the AE page in addition to being reported as SAEs).

MS relapses that, in the view of the investigator, warrant specific notice due to unusual frequency, severity or remarkable clinical manifestations (these should be reported as AEs on the AE page of the eCRF and, if applicable, on the SAE form).

Additionally, the following assessments must be done during those visits:

- Recording of changes in concomitant medications
- Recording of AEs and SAEs
- Schedule an appointment for next visit, unless already done and instruct subject to:
 - Preferably come fasted to the site and contact their principal investigator / treating neurologist at the clinical site immediately in the event of the appearance of any symptoms suggestive of an MS exacerbation.

If a relapse visit is within 5 days prior to the date of a regular visit where MRI is assessed, efforts should be made to perform the MRI assessments prior to the start of treatment with i.v. corticosteroids. However, if this is not possible, then the MRI should be delayed until at least 14 days after the last dose of corticosteroids.

These visits for relapses are additional unscheduled visits. The regular scheduled study visits must be resumed according to the original visit and assessment schedule. If the visit is within the visit window of a regular visit, the assessments for the relapse unscheduled visit count as the ones of this regular visit.

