5.2.1 Recommended concomitant therapy

Treatment of relapses:

- If a relapse requires treatment with corticosteroids, methylprednisolone 1 g i.v. daily for 3 to 5 days is recommended. Treatment with other corticosteroids, another dose, other routes of administration, or adrenocorticotropic hormone (ACTH) is not recommended unless deemed absolutely necessary, and must be documented in the subject charts by the investigator. Oral taper with corticosteroids is not permitted.
- Treatment of relapses with plasma exchange (i.e., plasmapheresis, cytapheresis) is prohibited.

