6.1.2 MRI-based endpoints

15 March 2022, page 86/216

Table 7 MRI-based endpoints

Endpoints	Combined Analysis Period	Extension Analysis Period
 PCBV at all assessments 	Y	Y
• CUAL, defined as new Gd+ T1 lesions plus new or enlarging T2 lesions without double-counting the lesions) at all assessments	Y	Y
• Number of Gd+ T1 lesions at all assessments	Y	Y
• Cumulative number of new or enlarging T2 lesions (relative to baseline) at all assessments	Y	Y
• Volume of MRI lesions (T2 lesions, T1 hypointense lesions) at all assessments	Y	Y
• Absence of MRI lesions (Gd+ T1 lesions, new or enlarging T2 lesions) at all assessments	Y	Y
 Proportion of Gd+ lesions at baseline evolving to PBHs at all assessments 	Y	Y

CUAL = cumulative number of combined unique active lesions; MRI = magnetic resonance imaging PBH = persistent black holes; PCBV = percent change from baseline in brain volume.

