Based on the interview and examination, the principal investigator / treating neurologist will determine if symptoms are likely to be due to a relapse (i.e., all elements from the relapse definition

15 March 2022, page 92/216

EDMS-ERI-207656619

EudraCT 2016-004719-10

Confidential

in Section 6.1 have been verified, in the absence of another, better explanation of the subject's symptoms), the subject will be referred to the efficacy assessor for an EDSS assessment (NB: at scheduled visits the EDSS assessment planned for this visit will be used). The completed questionnaire and the outcome of the examination will be collected in the eCRF.

Step 3: The efficacy assessor will perform the EDSS/FS assessment within 7 days of the onset of new or worsening neurological symptom(s) [see Section 7.4.1]. Important note: EDSS and FS assessments will be performed only by the efficacy assessor. The efficacy assessor must not consult prior EDSS/FS scores when performing the current EDSS/FS assessment. In no case will the treating neurologist alter the EDSS/FS score obtained by the efficacy assessor. If the relapse requires treatment with corticosteroids [see Section 5.2.1], treatment should be initiated as early as recommended by local clinical practice. The neurological examination by the efficacy assessor must always be performed prior to the treatment start.

Step 4: The treating neurologist will review the EDSS/FS score obtained by the efficacy assessor and determine presence or absence of qualifying increase in EDSS/FS (i.e., of the magnitude described in Section 6.1 from a previously clinically stable EDSS/FS score and consistent with the subject's new symptoms). Based on this review, the treating neurologist will decide if the relapse is confirmed or not, according to the protocol definition of confirmed relapse [see Section 6.1].

[figure not shown]
Once step 1 of the relapse detection has been initiated (whether by subject calling the site, by interview of the subject at scheduled visit, or by scheduled calls from the site to the subject), the final result of the relapse detection and confirmation process will be captured as one of the following three outcomes: no relapse, unconfirmed relapse, or confirmed relapse. New or worsened neurological symptoms reported by the subject and for which there is another and better explanation for the subject's current symptoms than an MS relapse will be captured on an AE page.

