8.3.8 Visits 6, 8, 9, 10, 12, 13, 14, 16, 17, 18, 20, 21, 22; Weeks 36, 60, 72, 84, 108, 120, 132, 156, 168, 180, 204, 216, 228

The visit window for these visits is \pm 14 days. The IRT call defines the date of the visit. All other assessments may be performed within the window of this visit date. The visits include:

- EDSS/FS
- MS relapse
- Recording of changes in concomitant medications
- Assessment and recording in the eCRF of methods of contraception (for WOCBP only)
- Body temperature
- SBP/DBP (pre-dose)
- Pulse rate (pre-dose)
- Hematology, blood chemistry, and (following approval of protocol version 5) a serum sample for immunogenicity evaluations (e.g., anti SARS-CoV-2 antibody testing) will be collected for all subjects
- Urinalysis
- Urine pregnancy test for WOCBP (NB: female subjects who interrupt the study treatment because of planned pregnancy will be exempted from any protocol-mandated pregnancy tests after the first positive pregnancy test and until 30 days before study drug re-initiation. Study medication accountability and compliance review
- IRT call and study treatment dispensing
- Recording of AEs and SAEs

15 March 2022, page 115/216

Confidential

EudraCT 2016-004719-10 EDMS-ERI-207656619

- Remind WOCBP and fertile men to use the methods of contraception defined for this study (for WOCBP throughout the study until at least 30 days after study treatment discontinuation and until 6 weeks after the first of two consecutive tests confirming plasma teriflunomide level <0.02 mg/L[#] and for fertile men, until 6 weeks after the first of two consecutive tests confirming plasma teriflunomide level <0.02 mg/L[#], if applicable). Schedule an appointment for next visit and instruct subject to:
 - Come fasted to the site (recommended)
 - Bring back all study treatment bottles
 - Not take study treatment on the day of study visit prior to coming to the site
 - Contact their principal investigator / treating neurologist at the clinical site immediately
 in the event of the appearance of any symptoms suggestive of an MS exacerbation.

Important note: Teriflunomide testing is no longer required with the approval of protocol version 5

8.3.9 Visits 7, 11, 15, 19 - Weeks 48, 96, 144, 192

The visit window for these visits is \pm 14 days. The IRT call defines the date of the visit. All other assessments may be performed within the window of this visit date. The visits include:

- EDSS/FS
- MS relapse
- MSFC
- SDMT
- SF-36 v2
- eC-SSRS
- MRI

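### The steroid rule for MRI is triggered only by a relapse visit within 5 days before the scan, which is too short for its own 14-day washout; few scans are affected

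*Protocol*

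**What the plan says.** Section 8.5.1 of the Protocol holds the only rule linking corticosteroids to MRI timing. Its condition reads: "If a relapse visit is within 5 days prior to the date of a regular visit where MRI is assessed". In that case the site should try to scan before i.v. corticosteroids start. If it cannot, "then the MRI should be delayed until at least 14 days after the last dose of corticosteroids". Both instructions hang on the 5-day condition. For all relapse visits, the section then gives the general default: "The regular scheduled study visits must be resumed according to the original visit and assessment schedule".

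On the steroids, Section 5.2.1 states that "methylprednisolone 1 g i.v. daily for 3 to 5 days is recommended", and Section 7.4.2 that "treatment should be initiated as early as recommended by local clinical practice". Section 8.3.9 sets a window of ±14 days for the visits at Weeks 48, 96, 144 and 192, and says: "All other assessments may be performed within the window of this visit date". Section 7.4.3 (MRI evaluations) adds no steroid rule and leaves detailed procedures to a separate MRI manual.

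The scans feed Table 7 of Section 6.1.2, which lists "Number of Gd+ T1 lesions at all assessments" and "CUAL, defined as new Gd+ T1 lesions plus new or enlarging T2 lesions without double-counting the lesions". The synopsis names CUAL among the main endpoints.

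**The concern.** A washout measured from the last steroid dose needs a trigger that reaches back at least as far as the washout plus the length of the course. This one reaches back 5 days. A subject whose relapse visit falls 5 days before the MRI visit must be scanned before steroids or wait 14 days after them. A subject whose relapse visit falls 6 days before has no such requirement, although the steroid course may have ended only days earlier.

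The protocol does not say why it has the washout. The natural reading is that a scan soon after steroids may not show the disease activity it is meant to measure. If so, the exposed scans are not a random sample: they come from subjects with a recent treated relapse. MRI is scheduled only every 48 weeks. CUAL is summed over all post-baseline scans (Section 11.3.1.4) and analysed with the log of the number of scans as offset (Section 11.4.5), so an affected scan counts like any other.

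**Working it through.** The plan gives no derived figure to reproduce. Its two stated numbers, 5 days and 14 days, stand in one paragraph of Section 8.5.1 and can be compared by counting days.

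**Inputs**
- Trigger: relapse visit 0 to 5 days before the MRI visit (Section 8.5.1).
- Washout: at least 14 days after the last dose (Section 8.5.1).
- Course length n: 3 to 5 days (Section 5.2.1).
- Assumption: steroids start on the day of the relapse visit and are given on consecutive days.

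**Gap from last dose to scan.** For a relapse visit d days before the scan, gap = d − (n − 1).
- d = 6, n = 3: 6 − 2 = 4 days.
- d = 6, n = 5: 6 − 4 = 2 days.
- A gap of at least 14 needs d ≥ 13 + n, that is d ≥ 16, 17 or 18 for n = 3, 4 or 5.

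**Days outside the trigger but inside the washout**

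| Course | Relapse visit, days before scan | Number of days | Last dose, days before scan |
|---|---|---|---|
| 3 days | 6–15 | 10 | 4–13 |
| 4 days | 6–16 | 11 | 3–13 |
| 5 days | 6–17 | 12 | 2–13 |

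The trigger covers 6 days (0 to 5). If steroids start k days after the relapse visit, the upper limit moves out by k: for k = 1 to 3 it becomes 16 to 18 (3-day course) or 18 to 20 (5-day course).

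**How many scans.** Further inputs:
- 800 subjects (Section 11.6).
- Five scans each: Weeks 48, 96, 144, 192 and end of treatment (Table 1), so 800 × 5 = 4,000 scans.
- Annualized relapse rate 0.15 (long-term phase 2 extension, ponesimod 20 mg) to 0.20 (core-study ponesimod arm, 0.202), both from Section 1.3.2.3.
- Assumption: every relapse is treated with steroids.

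Expected scans = 4,000 × uncovered days × rate / 365.25.
- Rate 0.15: 4,000 × 10 × 0.15 / 365.25 = 16.4; with 12 days, 19.7.
- Rate 0.20: 4,000 × 10 × 0.20 / 365.25 = 21.9; with 12 days, 26.3.
- Share: 16.4 / 4,000 = 0.4% to 26.3 / 4,000 = 0.7%.
- If half of relapses are treated: about 8 to 13 scans.

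**Delay against the visit window.** Where the present rule applies, the earliest delayed scan falls (n − 1) + 14 − d days after the target date. For d = 0 this is day +16 (3-day course) or +18 (5-day course), outside ±14. It exceeds +14 for d = 0 to 1 (3-day) or d = 0 to 3 (5-day). For the newly covered days, d ≥ 6, it is at most 2 + 14 − 6 = +10 or 4 + 14 − 6 = +12. Widening the trigger therefore adds no overrun when the regular visit is on its target date and steroids start at the relapse visit.

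**The case against.** The case for leaving the text alone has several good parts.

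- **The site may move the scan.** The ±14-day window allows it. Section 8.5.1 also lets a relapse visit inside a regular visit's window count for that visit, so for relapse visits 6 to 14 days before the target date a pre-steroid scan is possible. This stands as a mitigation, but it is permission only. MRI is not among the assessments that Section 8.5.1 lists for a relapse visit, and nothing tells the site to delay. A reader might infer that these subjects are bound to be scanned inside the washout. The text supports only that no delay is required.
- **NEDA.** A reader might infer that a suppressed scan would falsely credit subjects with NEDA-3 or NEDA-4. Section 6.1.1 rules this out for the scans counted here, because a confirmed relapse already fails both. Only a steroid-treated relapse that was never confirmed could matter.
- **A higher rate.** Using 0.29 per year would raise the count, but that is the core-study teriflunomide rate, and everyone in the extension takes ponesimod.
- **Completeness.** Not all subjects will have five scans: treatment can end early, and some end-of-treatment scans are waived. The counts above lean high for this reason.
- **The MRI manual.** It is not shown and may hold a broader steroid rule. Section 8.5.1 does not refer to it on this point.
- **Mechanism.** The protocol states neither the size nor the direction of any steroid effect, including on brain volume, and CUAL also counts new or enlarging T2 lesions. The study is descriptive, with no hypotheses (Section 11.4.1).
- **Timing.** Section 7.8 gives a mean of 10 remaining visits on 3 June 2021 among subjects with more than one left, so by Version 6 (March 2022) few scheduled scans remained for a prospective change.

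These points limit the consequence. They do not reconcile the trigger with the washout.

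**Conclusion.** The point holds in a limited form. Section 8.5.1 sets a 14-day washout and then applies it through a 5-day trigger, leaving 10 to 12 days of relapse visits (days 6–15 or 6–17 before the scan) where its own standard is not required. The day count rests on a 3 to 5 day course starting at the relapse visit; a later start widens the gap.

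The size is small: about 0.4 to 0.7% of scans under the assumptions above, and less with early ends of treatment or untreated relapses. It falls mainly on Gd+ T1 counts and the Gd+ part of CUAL, in recently relapsed subjects. The documents do not support a claim that the efficacy picture as a whole, NEDA, or the comparison by core treatment is materially biased. The reason to act is that the inconsistency is plain, the affected scans are not random, and the correction costs little.

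**What to change.** 1. In Section 8.5.1, tie the MRI-timing rule to the date of the last i.v. corticosteroid dose for a relapse, in place of the 5-day relapse-visit condition: scan before the first dose where possible, otherwise at least 14 days after the last. Check that the MRI manual agrees.
2. State that scans delayed under this rule at Weeks 48, 96, 144 and 192 may fall outside the ±14-day window. The present rule already leads there for relapse visits close to the MRI visit.
3. Treat the end-of-treatment scan separately. Section 3.2.3.1 places that visit no later than 14 days after the last study dose, so a longer delay could put the scan off study drug or on commercial ponesimod. Scan before steroids where possible; otherwise keep the scan in its window and flag it.
4. For all scans, including those already done, flag those within 14 days after steroids, using the start and stop dates already collected under Section 7.3. Repeat the Gd+, CUAL and brain-volume summaries without them as a sensitivity analysis. With few scheduled scans left, this is the more useful step. It can sit in the SAP; its absence from the protocol is not the fault raised here.

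The cost is a few later scans, a short text change and one extra sensitivity table. Steroid treatment of relapses is unchanged.

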8.5.2 Unscheduled visits (any other assessment; U1, U2, U3, etc.)

An unscheduled site visit may be performed at any time during the study (between scheduled visits), as necessary, at the investigator's discretion. The date of the visit and the reason for such visits as well as any data related to study assessments performed at unscheduled visits will be recorded in the eCRF. During such visits, any of the following assessments may be performed at the investigator's discretion:

- EDSS/FS
- MS Relapse (if the subject is meeting the principal investigator / treating neurologist)
- MRI
- Assessment of concomitant medications
- Assessment of methods of contraception (for WOCBP only)
- Physical examination
- Dermatological examination
- Body temperature
- Body weight
- SBP/DBP

15 March 2022, page 121/216

Confidential

EudraCT 2016-004719-10 EDMS-ERI-207656619

- Teriflunomide plasma concentration[#]
- Pulse rate (to be assessed only if no 12-lead ECG is performed)
- Ophthalmological examination (e.g., presence of visual symptoms suggestive of active uveitis [see Section 5.1.12.7])
- OCT (e.g., presence of visual symptoms suggestive of macular edema or active uveitis [see Section 5.1.12.7])
- Complete laboratory tests including: hematology, blood chemistry, viral serology, urinalysis, urine or serum pregnancy test (for WOCBP only).
- IRT call return of study treatment bottles and unused medication, and dispensing of new bottles, if appropriate.
- Assessment of AEs and SAEs.

Important note: Teriflunomide testing is no longer required with the approval of protocol version 5

Additional unscheduled spirometry will have to be conducted in the event of respiratory symptoms (e.g., dyspnea) and in the event of FEV₁ or FVC at a scheduled visit showing decrease from extension study baseline by >30% during the course of the study. Administration of inhaled short-acting $\beta 2$ agonist (e.g., albuterol/salbutamol) for symptom relief may be performed at the discretion of the investigator. Administration of short-acting $\beta 2$ agonist will be collected in the eCRF.

If any of the laboratory variables listed in Section 7.5.12.2 need to be analyzed, this must be done at the central laboratory, except in case of emergency; if it has been done at a local laboratory, results must be recorded in the eCRF [see Section 7.5.12].

